10. CLINICAL SUPPLIES

10.1 Study Medication and Dosage

The Sponsor will supply the following study medication for administration:

Table 2. Study Medication

Treatment Group	Contents of Metered Spray Bottle
CTY-5339 Anesthetic Spray 1 spray (\approx 200 μ L total)	14.0% Benzocaine, USP = 28 mg 2.0% Tetracaine Hydrochloride, USP = 4 mg
CTY-5339 Anesthetic Spray 2 spray (\approx 400 μ L total)	14.0% Benzocaine, USP = 56 mg 2.0% Tetracaine Hydrochloride, USP = 8 mg
CTY-5339-CB 1 spray (\approx 200 μ L total)	14.0% Benzocaine, USP = 28 mg
CTY-5339-P 1 spray (\approx 200 μ L total)	Vehicle control (no active ingredient)

10.2 Packaging and Labeling

All study medication bottles will be labeled according to the FDA guidelines. In order to maintain the double-blind conditions for all treatment groups, the person(s) preparing and administering the test treatments will be different from the person(s) doing the clinical efficacy evaluations. A randomization list generated by the Statistics Group will list the investigational product(s) to be assigned to each subject during each treatment session, and which cheek (left or right) the study medication should be applied to. Subjects will be numbered starting from 101.

Study medication for subjects randomized to receive CTY-5339-A one spray in one treatment session and CTY-5339-CB one spray in the other treatment session will be double-blinded and packaged individually. Study medication for each subject will consist of 2 bottles, one bottle containing CTY-5339-A, and one bottle containing CTY-5339-CB. Each bottle will be labeled with the appropriate treatment session (A or B) and which cheek the study medication should be applied to (left or right), according the randomization schedule. The two bottles will be packaged in a box. Each bottle will be primed three times immediately prior to use.

Study medication for subjects randomized to receive CTY-5339-A two sprays in one treatment session and CTY-5339-CB one spray and CTY-5339-P one spray in the other treatment session will be packaged in bulk. The label for each bottle will contain the identity of its contents (CTY-5339-A, CTY-5339-CB, or CTY-5339-P). The person preparing and administering the test treatments will use the randomization list generated by the Statistics Group to apply the appropriate product to the appropriate cheek, and the appropriate area(s) of the cheek. The bottle will be primed three times prior to each use.

Another randomized listing generated by Statistics Group that has the same treatment assignments will be sent to the appropriate party responsible for packaging and labeling the study medications.

In addition, a master code will be kept by the Sponsor and at the study site. The study site master code will have individually sealed envelopes identifying the drug in each bottle for each patient enrolled in the study. The treatment for an individual subject may be unblinded in the event of an emergency and only if medically necessary without breaking the code for any other subject. Procedures to be followed for unblinding, notification responsibilities, and regulatory requirements are detailed in Section 12.4.5.

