APPENDIX 1: DESCRIPTION OF TESTING METHODS

Appendix 1A: Pin Prick Test (PPT)

Oral Mucosa sensation directly over the circumscribed sites will be assessed with a 90-mm, 26-gauge pencil-point spinal needle (Polymedical; Temena S.A., Bondy, France or its equivalent) at Screening, Baseline and predetermined intervals after application of drug. To standardize the methodology, all tests are performed by holding the needle at its hub and orienting it perpendicular to the oral mucosa surface. Pressure is applied until the needle shaft bows slightly. At screening a numerical score on a 0 – 10 pain intensity scale (NRS) is recorded for each cheek. After study drug administration, subjects are instructed to rate the pinprick sensation perceived over the circumscribed treatment site compared to that perceived at the contra-lateral circumscribed, non-treated site and to report the sensation as none, less, or similar/more to the non-treated site. Reports of none or less indicate analgesia, while a report of similar/more indicates complete regression of analgesia. At each observation, 3 pin pricks are performed first on the non-treated side, and then on the treated side. For each cheek, the first pin prick will not be used for analysis. Of the remaining two pin pricks, the one with the most severe pain rating will be used for the data analysis.

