12.4.5 Breaking the Blind

A set of tamper-proof sealed individual envelopes containing the bottle numbers on the outside of the envelope and the treatment code inside the envelope, will be sent to the investigative site. In the event of a medical emergency that necessitates breaking the code, the sealed envelope containing the treatment code may be opened. The seal will only be broken by the Investigator in the event of an emergency for which knowledge of the subject's double-blind investigational product will have a direct impact on treatment decisions. Every effort will be made to discuss the decision to break the blind with the Cetylite Medical Monitor in advance.

When the blind is broken, the Investigator will notify the Sponsor's Medical Monitor immediately in order to document the reason and date of the unblinding. The event will also be recorded on the CRF and in the source document. The Investigator will submit a written explanation to the Sponsor describing the event within 5 business days.

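### In the two-spray sequences, bulk bottles show their product code and nothing keeps them from the view of the subject, who rates both efficacy tests; the bottle-number key on the code-break envelopes does not fit bulk supply

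*Combined protocol and SAP*

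**What the plan says.** Section 10.2 describes two supply systems.

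- **One-spray sequences** (CTY-5339-A one spray and CTY-5339-CB one spray). The medication "will be double-blinded and packaged individually", two bottles per subject. On labelling: "Each bottle will be labeled with the appropriate treatment session (A or B) and which cheek" is to be treated.
- **Two-spray sequences** (CTY-5339-A two sprays, and CTY-5339-CB plus vehicle CTY-5339-P). The medication "will be packaged in bulk". On labelling: "The label for each bottle will contain the identity of its contents", given as one of the three product codes. The administrator picks the bottle from the randomization list. On re-use: "The bottle will be primed three times prior to each use".

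Blinding rests on the separation of people. The Synopsis and Sections 9, 10.2 and 10.3 have the drug given by a third party or delivery team distinct from the evaluators; Section 10.3 extends this to other study personnel.

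The readings come from the subject. For pin prick, Appendix 1A says "subjects are instructed to rate the pinprick sensation perceived over the circumscribed treatment site" against the untreated side. For heat, Appendix 1B has the subject press a mouse at the first sensation.

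For code-breaking, Section 10.2 describes sealed envelopes at the site that identify the drug in each bottle for each patient, and requires that one subject can be unblinded without revealing any other. Section 12.4.5 describes the same set as "containing the bottle numbers on the outside of the envelope", with the treatment code inside.

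**The concern.** The separation of dosing team and evaluators protects a person who records the outcome, not the person who generates it. With a comparative pain rating and a self-terminated heat stimulus, the blind that matters most is the subject's. The vehicle spray exists so that the control session in the two-spray sequences also has two sprays. A bottle that names its contents, or a visible change of bottle between sprays, works against that purpose. If subjects form a view about which session held the combination, their ratings can shift, and no analysis can undo that afterwards.

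The envelope issue is separate and smaller. An envelope identified by a bottle number works when a bottle belongs to one subject and one session. It does not work when one bottle serves many.

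**Working it through.** The plan gives no figure for this point. The only arithmetic is a count of scope; the rest is a comparison of sections.

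**1. Scope.** Inputs from the Synopsis (number of subjects): 76 subjects, 152 exposures, 38 exposures for each CTY-5339-A regimen, 76 for CTY-5339-CB. The sequence table gives each subject one CTY-5339-A session and one control session.

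- Two-spray subjects: 38 two-spray exposures, one per subject = 38 of 76 (50%).
- Their sessions: 38 (CTY-5339-A, two sprays) + 38 (CTY-5339-CB plus CTY-5339-P) = 76 of 152 (50%).
- One-spray sessions: 152 − 76 = 76, in 76 − 38 = 38 subjects.
- Check on control exposures: 38 (one-spray sequences) + 38 (two-spray sequences) = 76, which is the plan's own figure.

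These counts ignore replacement subjects.

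**2. Who is shielded.**

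| Person | Role in the outcome | Safeguard stated |
|---|---|---|
| Evaluator | Applies the stimulus | Separate from the dosing team (Synopsis, Sections 9, 10.2, 10.3) |
| Subject, one-spray sequences | Gives both readings | Blinded bottle labelled by session and cheek (Section 10.2) |
| Subject, two-spray sequences | Gives both readings | None for the bottle or label; a vehicle spray equalizes the number of sprays (Synopsis, Section 9) |

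**3. What a subject could learn.** The label carries product codes, not drug names. A subject need not decode them to notice a difference. One session uses a single product; the other uses two products with different labels, and the vehicle is sprayed outside the marked circle. Because the same subject attends both sessions, the contrast is available if bottles are in view. The documents do not say whether they are.

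**4. Which comparisons are exposed (Sections 8.3 and 13.5).**

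| Comparison | Supply |
|---|---|
| Primary: A one spray vs CB one spray | Both individually packaged and blinded |
| Secondary: A two sprays vs CB plus P | Both from content-labelled bulk bottles |
| Secondary: A two sprays vs A one spray | One arm bulk, one arm blinded |
| Secondary: onset and responder rates, where they involve the two-spray sequences | Bulk for those sessions |

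**5. Envelopes.** Section 10.2 gives bulk bottles a contents label and mentions no number or subject-specific label. Bulk packing and priming before each use point to a bottle used repeatedly. That bulk bottles have no subject-specific number is therefore an inference, not a statement in the text. If they do carry a number, it still would not single out one subject and session, and the bottle's contents are already on its label. A bottle-number key (Section 12.4.5) thus does not fit this half of the supply, while the per-patient description in Section 10.2 does.

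**The case against.** The strongest reply is that unblinding is assumed, not shown. No section says that a subject can see the label during a spray to the inner cheek, or knows what the codes stand for. The consent text is not available for review, so what subjects are told about the codes cannot be checked. This stands: the documents support a risk, not an event.

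The second reply is that an unmasked administrator is a deliberate choice. CTY-5339-CB goes inside the circle and the vehicle outside it, so the dosing team must know which bottle is which. This also stands, but it does not require the subject to see the contents; a code list serves the same need.

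Third, neutral codes alone would not hide the change between two bottles, nor keep the product from dosing staff. That is correct, and it is why the fix has to cover sight of the bottles and disclosure as well as the label. The place where the vehicle lands remains a possible cue that labelling cannot remove.

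Two stronger readings are tempting. A reader might infer that the primary result is compromised, because the Synopsis speaks of a single CTY-5339-CB group and counts its 76 exposures together. The documents do not support this: the primary comparison is one spray against one spray, and CTY-5339-CB plus vehicle is named separately among the secondary comparisons. The exposure would reach the primary only if the two control conditions were pooled. A reader might also infer that emergency unblinding fails for half of the subjects. It does not: the sponsor and the site hold the master code, and the administrator works from the randomization list.

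**Conclusion.** The point holds as a risk to the subject's blind in the two-spray sequences: 38 of 76 subjects and 76 of 152 sessions. It concerns secondary comparisons in a proof-of-concept study. Neither the probability that a subject is unblinded nor the bias that would follow can be derived from the documents. The primary comparison is untouched as defined, on the condition that the control sessions with vehicle are not pooled into it.

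It is still worth acting on. The open label is a stated rule rather than an omitted detail, the other half of the trial already has blinded bottles, and the outcome is subjective. The envelope point is a mismatch between Section 10.2 and Section 12.4.5, limited to how envelopes are identified; it rests on the inference that bulk bottles are shared across subjects.

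**What to change.** 1. In Section 10.2, mask the bulk bottles with an opaque sleeve or a neutral code, and keep the contents on the dosing team's list only.
2. In Sections 10.2 and 10.3, require that bottles and labels, including the change from CTY-5339-CB to CTY-5339-P, stay out of the subject's sight, and that dosing staff do not disclose the product. This item is essential; item 1 alone does not hide the switch.
3. Reconcile the supply and envelope text of Section 10.2 with Section 12.4.5: key each sealed envelope to subject number and session, so that opening one reveals one subject's treatment only.

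The cost is relabelling the bulk bottles and envelopes, plus a code look-up by the dosing team before each spray, which makes a clear list necessary to avoid selecting the wrong bottle. Endpoints, sample size and treatment regimens are unchanged.

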10.3 Assignment of Study Medication

Treatment assignments will be determined by a computer-generated randomization schedule maintained by the Statistics Group.

The randomization schedule will randomly assign one of the four treatments (CTY-5339-A one spray, CTY-5339-A two sprays, CTY-5339-CB one spray, or CTY-5339-CB one spray plus CTY-5339-P one spray) to the appropriate area(s) of the cheek mucosa. For PPT assessments, the untreated, control area on the contra-lateral side will always receive the stimulus assessment first.

Randomization numbers will be assigned in a sequential order starting from 101. A drug delivery team (different for the evaluators or other study personnel) will administer the treatments to the cheek mucosal area.

The randomization number assigned to the subject will be recorded in the CRF.

10.4 Administration of Study Medication and Duration of Evaluation

Each subject entered into the study will be given the randomly assigned study medications in the assigned circumscribed areas of the cheek mucosa at Baseline (Time = 0 hour). The duration of in-house treatment evaluations will last up to 60 minutes. The same team of coordinators and/or investigators will do all the evaluations.

10.5 Study Medication Accountability

10.5.1 Storage

All materials for this study must be stored in an area free from environmental extremes in a locked closet and with restricted access. A Cetylite representative will inspect the study medication storage area and discuss the study medication accountability system with the PI and site coordinators prior to shipment of the study medication to the site.

10.5.2 Study Medication Inventory

Upon receipt at the study site, the carton containing the study medication supplies will be stored unopened in the study medication storage room. At the study initiation, the PI or an appropriate designee, and a representative of Cetylite will conduct an inventory and complete the study medication inventory record. The original will be sent to Cetylite, and the PI will retain a copy. Any interim shipments will be inventoried by the PI or his/her designee. For all interim shipments, a study medication inventory record will be completed. The original will be returned to Cetylite, and the PI will retain a copy.

The PI or an appropriate designee, upon dispensing the study medication, must record the information on a study medication dispensing/return log. For accounting purposes and assessing subject compliance, a representative of Cetylite will review the study medication dispensing/return log, inventory the study medication, and inspect the storage facility at appropriate time intervals throughout the clinical investigation, depending on the length of the study. The PI must account for any discrepancy and/or deficiency.

10.5.3 Return of Study Supplies

All unused study medication shipped for this clinical trial will be returned to the Sponsor at the termination of the study. At the conclusion of the study, the PI or an appropriate designee, and a representative of Cetylite will inventory all used and unused study medication. The study medication inventory record for returned study medication will then be completed. Cetylite will retain the original, and the Investigator will retain a copy for his files.

All unused study medication will then be returned to:

Cetylite Industries, Inc.
[name]
Attention: Returned Study Supplies
Protocol No. C-002

Upon receipt at Cetylite, a letter acknowledging the receipt of returned materials and a copy of the Study Medication Inventory Record will be sent to the Cetylite Medical Monitor.

11. STUDY PROCEDURES

11.1 Study Conditions

- a. Only subjects who satisfy all inclusion and exclusion criteria and provide written informed consent may participate in the trial;
- b. Subjects will remain at the study site for up to 2 hours at each of two test sessions.
- c. Subjects will be tested in the same room and by the same coordinator team at each evaluation time point during both 1hour test sessions.

11.2 Schedule of Assessments

11.2.1 Screening Assessments

During the screening period, the PI or his designee will examine each subject and complete a checklist of the inclusion and exclusion criteria (see Sections 9.2 and 9.3, respectively) in order to determine the subject's eligibility. The Investigator or study coordinator will enter the pertinent historical information (including any medication taken recently) and clinical findings (including blood pressure) in the appropriate section(s) of the source documents.

A Subject Screening Log (provided by Cetylite) will be maintained in the site central file to document all subjects screened for entry into the study. Subjects will be screened only once. All subjects who meet the entrance criteria will provide written informed consent before participating in the study. Subjects are required to read, comprehend, and sign the informed consent. The screening procedure will also include evaluation of:

- a. PPT and QST heat sensation assessments of each cheek
- b. Vital signs (pulse rate and blood pressure in supine or reclining position, body temperature) and pulse oximetry (must be \geq 96%)
- c. Safety bloods including section Clinical chemistry (Sodium, Potassium, Creatinine, AST, ALT, Alkaline Phosphatase, LDH and Bilirubin), Hematology (Hemoglobin, Hematocrit, Thrombocytes, Erythrocytes and Full blood differential)
- d. Urine drug screen and pregnancy test

e. 12 lead ECG (PR, QRS, QT interval, heart rate and rhythm)

Appropriate screening information for eligible subjects who are assigned a subject number and receive study medication will be transcribed onto the corresponding sections of the CRF. The experiment must occur within 30 days of the screening visit.

The following will be noted and recorded on the CRF:

- Date and time the drugs treatments were initiated and completed
- Any vital signs obtained (require blood pressure)

11.2.2 Baseline Assessments

After confirming continued eligibility, Baseline ECG, vital signs, and blood sample will be obtained. In addition, tissue site evaluations will be performed. The area of the treated cheek is circumscribed using an oral indelible pencil. Prior to drug administration, the presence or absence of pain after the PPT (using a 90-mm, 26-gauge pencil-point spinal needle), will be evaluated on both cheeks. Heat sensation threshold (using QST) will be assessed in the circumcised area of the to-be-treated side of the cheek. These baseline data will be recorded on the CRF. The drug will then be administered onto the assigned circumscribed area. In order for a subject to be eligible to continue in the study, the last 2 of the 3 baseline PPT scores must be at least “3” or higher, and 1 must be “4” or higher. The mean of the last 2 of the 3 baseline temperature assessments must be 48.5°C or less.

11.2.3 Post-Baseline Assessments

The time points of the post-baseline efficacy assessment are detailed in section 9 of this protocol. The PPT will be performed on both the control and treatment sites at each evaluation time point. The QST will be performed only at the treatment site for the post baseline evaluation time points.

11.3 Efficacy Assessments

11.3.1 Pin Prick Test (PPT)

Oral mucosal sensation directly over control and drug sites will be assessed with a 90-mm, 26-gauge pencil-point spinal needle (Polymedic; Temena S.A., Bondy, France or its equivalent) at Baseline and predetermined intervals after application of drug. To standardize the methodology, all tests are performed by holding the needle at its hub and orienting it perpendicular to the oral mucosa surface. Pressure is applied until the needle shaft bows slightly. For each test, the subject is instructed to rate the pinprick sensation perceived over the treatment sites compared to that perceived at the contra-lateral non-drug site, and to report the sensation as none, less, or similar/more to the treated site. Subjects will rate pain at the control site on a 0-10 Numerical Rating Scale with “0” as no pain and “10” as severe pain. Reports of none or less at the treatment site indicate analgesia, while a report of similar/more indicates complete regression or absence of analgesia.

At each observation, 3 pin pricks are performed at each site, first at the non-treated cheek and then at the treated cheek. The first pin prick is not used for analysis. Of the remaining 2 pin pricks, the one with the most severe pain rating is used for the data analysis.

11.3.2 Heat Sensation Tolerance

This procedure uses the QST Heat Stimulator, a commercially available thermo-sensory analyzer that delivers heat stimuli to the oral mucosa with a blunt thermode that is 6mm in diameter. A central unit generates and transmits the signal to the thermode. This signal is controlled by proprietary software stored on a laptop connected to the central unit. Also attached to the central unit is a hand-held control that allows a study subject to stop the heating of the thermode. The heat is applied in graded increments until the subject first reports either tingling, warmth, heat, or pain or the temperature reaches the maximum of 51°C (Note: Hot beverages such as tea and coffee are frequently served at temperatures between 50°C - 60°C.²⁵)

The heat stimuli are delivered, in 3 repetitions, with inter-stimulus intervals of 30s. The basal thermode temperature is set at a comfortable 35°C. The rate at which the thermode heats up is set at 0.5°C/s, while the rate at which it cools down is set at 8°C/s. The maximum thermode temperature is set at 51°C. The first stimulus is discarded and the remaining 2 stimuli are then averaged (unless the first two stimuli reach the maximum of 51°C). All tests will be done near the center of each circumscribed area, but in a different place at each evaluation time point.

